Randomization Procedures. For Aim 2, we will use an adaptive randomization procedure (urn randomization) to balance confounding variables among participants in each condition. Factors on which the adaptive randomization procedure will operate are viral load and self-identified gender. Computerized urn randomization will use an adaptation of Microsoft Access application gRand (used by Co-I [name]). Efforts will be made to keep the project coordinator (PC) blind to condition, therefore, PI [name] will randomize participants. Participants will be randomized following consent and baseline assessment (to determine severity of symptoms for the urn) to one of two conditions: (1) CPT-L + Standard of Care (SOC) or (2) Lifesteps + SOC. Within 7 days of interview and PI's randomization, the PI will contact the participant to inform him/her of condition. Case managers will do phone check-ins between sessions to encourage attendance and provide referrals and information to individuals in both CPT-L and Lifesteps groups. Individuals in the Lifesteps condition will receive the one-session adherence intervention in addition to any other standard treatment that a PLWH with PTSD symptoms would typically receive at a HIV care clinic. SOC treatment will vary in type, duration, and frequency (e.g.,

spiritual counseling, crisis hotline phone call, resource help for case manager,), but will be measured carefully across both conditions through coding of chart review and weekly electronic dairy assessment of service utilization (methods used successfully by Co-I [name] in prior RCTs) to account for Treatment dosage. Baseline, post-intervention and follow-up assessments will be collected by the PC. In the CPT-L condition, the PI, assigned case manager, and project therapist will make contact within 7 days of randomization. Participants in the control condition will be contacted by one of the Lifesteps-trained HIV care case managers.

Figure 2. Participant Flow Diagram

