In addition to feasibility, efficacy and adherence outcomes will aid in development of the subsequent R01. Parameter and variability estimates of efficacy outcomes will be derived from appropriate statistical models. Specifically, HIV symptom distress (physical and mental), CD4 cell counts, viral load, clinic attendance and ART adherence will be measured at pre- and post-intervention and 3-month follow-up. Proportion of participants with Clinic attendance (yes/no), ART adherence (yes/no), and detectable viral load at the end of treatment and follow up will be compared between study groups using a modified Poisson regression approach with a robust sandwich variance estimator. Initial analytic models for binary outcomes will include the primary treatment effect, study visit and interaction of study visit and treatment as well as variables used to balance the randomization procedure. Adjusted models will explore the additional baseline covariates significantly associated with outcomes. The proportion successful in each treatment group at each visit, the relative risk of success and associated 95% confidence interval will be reported. We anticipate that treatment will decrease CD4 cell counts and HIV

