symptom severity more so in the CPT-L group compared to Lifesteps at the follow up clinic visit. Treatment group differences will be assessed using generalized linear models adjusted for baseline cell counts/symptom scores. Normality of model residuals will be assessed using Q-Q plots and data transformations will be performed as needed. The CAPS-5 and PCL will examine PTSD severity at baseline, post-intervention and 3-month follow-up. The PCL will be assessed weekly during study intervention and follow-up. Rates of change from baseline to post-intervention and follow up will be estimated with generalized linear mixed effects regression models. Linear slope trends over time and associated standard errors will be calculated for each treatment assignment using a single model for all data. Estimated CAPS, PCL, and HIV symptom severity scores and associated standard error estimates will be calculated for each study group at each study visit and effect size estimates (Cohen's  $d$ , partial eta) will be tabulated and reported. As PCL scores are measured weekly, non-linear mixed effects models will be fit to not any cubic or quadratic trends that occur during study treatment and estimates of when treatment efficacy begins to show changes in effect size will be assessed and reported.

Exploratory investigations of substance use/misuse will be collected using the AUDIT and DAST. Changes in the proportion of participants reporting substance use between groups following study treatment and follow-up will be compared using modified Poisson regression models adjusted for baseline use and study treatment. Continuous AUDIT and DAST scores will be assessed in those who report use and compared between groups using generalized linear mixed effects models. Depression will be assessed at the same time points using the PROMIS Emotional Distress-Depression short form. Both raw and prorated T-scores will be assessed at each timepoint and treatment group comparisons will be made using generalized linear mixed effect models, adjusted for baseline PROMIS scores and study visit. Exploratory models will be adjusted variables used to balance the randomization procedure and those correlated with study outcomes. Secondary analysis of additional measures (QOL, HIV Stigma, Intersectional Stigma, ERQ) will be assessed between study groups using appropriate statistical methods. Analyses will be conducted using SAS version 9.4 (SAS Institute, Cary, NC, USA).

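### The prespecified models for ART adherence and clinic attendance leave out the baseline value of the outcome, at some cost in precision and exposure to chance imbalance

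*Combined protocol and SAP*

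**What the plan says.** All analysis text cited here is in section 12.0, Sample size, Statistical Power and Analysis, under Data Analysis Aim 2.

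- **Outcomes.** The groups are compared on "Proportion of participants with Clinic attendance (yes/no), ART adherence (yes/no), and detectable viral load at the end of treatment and follow up" by modified Poisson regression with a robust variance.
- **Initial model.** "Initial analytic models for binary outcomes will include the primary treatment effect, study visit and interaction of study visit and treatment". The sentence goes on to add the factors used to balance randomization. Section 10.0 names these: "Factors on which the adaptive randomization procedure will operate are viral load and self-identified gender".
- **Further covariates.** "Adjusted models will explore the additional baseline covariates significantly associated with outcomes".
- **Baseline data.** The plan says that "clinic attendance and ART adherence will be measured at pre- and post-intervention and 3-month follow-up". Table 2 marks self-reported ART adherence at baseline, post and 3 months, and appointment adherence at baseline and 3 months.
- **Other outcomes in the same section.** For CD4 and symptom scores: "Treatment group differences will be assessed using generalized linear models adjusted for baseline cell counts/symptom scores". For binary substance use: "modified Poisson regression models adjusted for baseline use and study treatment". The PROMIS depression model is also adjusted for its baseline score.

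**The concern.** Baseline status is a natural candidate for a strong predictor of later adherence or attendance. Inclusion criterion 6 accepts any one of five HIV-care problems, and low self-reported adherence is only one of them, so some participants can enter adherent and others not. The urn does not balance on adherence or attendance. With 30 per arm, a sizeable baseline gap between groups can easily arise by chance, and a model without the baseline value carries part of it into the treatment estimate.

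The substance-use model is the telling comparison. It is an exploratory binary outcome, analysed by the same method, and it is baseline-adjusted. ART adherence and attendance are named in the Aim 2 hypotheses and are not. No reason is given for the difference. What is at stake is the quality of the effect and variability estimates that the pilot is meant to hand to the next trial.

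**Working it through.** **Inputs from the documents.** 30 per arm; 95% intervals; planning rates of 10% and 20% for detectable viral load; stated half-width of 18 points.

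**Assumptions, not in the documents.** Let φ be the correlation between the binary outcome at baseline and at follow-up, taken as 0.2 to 0.6. Baseline adherence is taken as 30% to 70%. The selection threshold is taken as p<0.05, since the plan names none.

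**Step 1: the plan's own figure.** 1.96 × √(0.1×0.9/30 + 0.2×0.8/30) = 0.179. This reproduces the stated 18 points and is an unadjusted figure. It was set for viral load and serves here only as a yardstick.

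**Step 2: precision by formula.** On the difference scale, adjusting multiplies the variance by (1 − φ²). The half-width becomes 17.9 × √(1 − φ²), and the equivalent unadjusted size is 30/(1 − φ²) per arm.

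**Step 3: simulation.** Modified Poisson with robust variance, 30 per arm, a single visit, no treatment effect, 50% prevalence, gender and viral load in the model (viral load unrelated to adherence), 1,500 trials per φ. The last two columns are the average relative risk in trials where baseline adherence favoured CPT-L by 10 points or more.

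| φ | Half-width (points) | Equivalent n per arm | Cut in variance of log RR | Baseline selected at p<0.05 | RR, no baseline term | RR, baseline term |
|---|---|---|---|---|---|---|
| 0.2 | 17.5 | 31.2 | about 0% | 33% | 1.04 | 0.98 |
| 0.3 | 17.1 | 33.0 | 7% | 62% | 1.12 | 1.01 |
| 0.4 | 16.4 | 35.7 | 14% | 86% | 1.16 | 1.01 |
| 0.5 | 15.5 | 40.0 | 18% | 98% | 1.18 | 1.00 |
| 0.6 | 14.3 | 46.9 | 34% | 100% | 1.23 | 1.01 |

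At φ = 0 the unneeded term raised the variance by about 3%. Type I error without the baseline term was 4.3% to 4.8% over φ = 0.2 to 0.6.

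**Step 4: how often imbalance arises.** Exact binomial, simple allocation of 30 per arm: a baseline gap of at least 10 points has probability 0.48 (baseline rate 30% or 70%) to 0.52 (50%). A gap of at least 20 points has probability 0.12 to 0.16. Without adjustment, about φ × gap carries over: a 10-point gap at φ = 0.3 gives 0.3 × 10 = 3 points.

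**Step 5: allowing for viral load.** If baseline viral load is related to adherence, it takes up some of the gain. With 27 per arm, 50% adherent at baseline and 60% at follow-up, and no viral-load term, the cuts were 3%, 12% and 28% at latent correlations of 0.4, 0.6 and 0.8. At 50% prevalence these correspond to φ = (2/π) × arcsin(ρ) = 0.26, 0.41 and 0.59. A further simulation with a viral-load term in the model gave about 2%, 9% and 28%, with baseline adherence selected in about 37%, 74% and 97% of trials. The gain is somewhat smaller in places but does not vanish.

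**The case against.** - **The main model is fixed in advance.** This stands. A reader might infer that significance tests choose the covariates of the main comparison. They do not: the initial model is prespecified, and selection applies only to the later models, which the plan describes as exploring further covariates.
- **Viral load is already covered.** This stands. A reader might extend the point to all three binary outcomes, but viral load is a randomization factor and so is in the model. A near-duplicate term would add little, and with 30×0.10 + 30×0.20 = 9 expected events per visit it could make the fit unstable.
- **Baseline may be a level of the visit term.** Outcomes are measured before the intervention, and proportions are reported at each visit. If baseline were a visit level, the interaction would be a change-from-baseline contrast and would remove imbalance. The wording on comparing groups at end of treatment and follow-up makes this unlikely but does not exclude it. It would still not equal adjustment: the contrast at each later visit stays unadjusted, and on the difference scale change has relative variance 2(1 − φ), which is 1.4 at φ = 0.3, against 1 − φ² = 0.91 with the covariate.
- **The selection rule works where it matters most.** Partly right. At high correlation it nearly always picks up baseline, and where it often misses, the precision gain is small. Between the two, at φ of about 0.3, it misses in roughly four trials in ten, and the average RR under imbalance is still 1.12.
- **Carry-over is ordinary sampling error.** Right over repeated trials. At 50% with 30 per arm the half-width is 1.96 × √(2×0.25/30) = 0.253, or 25 points, so a 3-point shift is small beside it. A reader might infer a biased or invalid test; type I error near 5% rules that out. The harm is conditional on the imbalance that actually occurs.
- **This is a feasibility pilot.** It has no formal power analysis, and its success criteria are recruitment, retention and missing data. That limits how much weight the point carries.

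**Conclusion.** The point holds for ART adherence and clinic attendance only. Their initial models omit a baseline value that is collected, and this differs without explanation from how the plan treats substance use, CD4 count, symptom scores and depression. The later adjusted models would restore it only inconsistently.

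The cost runs from negligible at a correlation near 0.2 to roughly a quarter or more of the variance of the log relative risk near 0.6. The estimate also shifts with any baseline gap that happens to arise. These sizes rest on an assumed correlation, an assumed prevalence near 50% and simple allocation in the imbalance figures. Urn balancing on viral load, or eligibility rules that narrow the spread of baseline adherence, would reduce them. The point is worth correcting before outcome data are analysed; it does not undermine the trial.

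**What to change.** 1. **ART adherence model:** add baseline ART adherence as a fixed, prespecified covariate beside the randomization factors, as the substance-use model does. Use the same instrument as the outcome, and state whether it enters as a percentage or as yes/no at the plan's 85% cut-off.
2. **Attendance model:** do the same, but first define baseline attendance. Table 2 describes coding at end of study, section 10.0 defines retention over a year, and no pre-baseline window is given. State the look-back window, the yes/no rule, and how participants admitted under criterion 6a (diagnosed within the last 3 months) are handled, since they lack a comparable prior record.
3. **Adjusted models:** replace selection by significance with a short list of covariates named in advance.
4. **Visit term:** state that the modelled visits are post-intervention and follow-up, with baseline as a covariate.
5. **Viral load:** add no term; confirm only that the randomization factor in the model is the baseline value.

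The cost is one extra term in each of two models, a short definition for baseline attendance, and a slight loss of precision (about 3% in variance in the simulation) if baseline turns out to predict nothing. No added visits or participants are needed.

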**Assessments and Data Collection Procedures.** The PC (blind to condition) will conduct the initial eligibility (baseline) diagnostic assessments and all study assessments. The CAPS will be audio-taped and study personnel will listen to a randomly selected 20% to ensure reliability of CAPS diagnosis over the course of the study. The PC will administer the battery in the HIV care clinic or remotely by phone to the participant, based on participant preference. All timepoints will be collected on all participants, even if they drop out of treatment. Pilot trials indicate that major assessments take between 1.5 – 2 hours to complete. Individuals will be given \$50 for completing the baseline interview, \$40 for attending the first session, then \$60 for post-intervention assessments and 20-minute exit interview after completion of CPT-L sessions (i.e., post intervention ~6 weeks after study enrollment); and a \$75 gift card for 3 month follow up surveys. Several questionnaires were drawn from the PROMIS common data elements and NIH sponsored repositories to promote data sharing (e.g., PROMIS depression and BRICS Social Determinants of Health). Participants will complete a brief electronic diary on a weekly basis to assess use of resources/additional supports. Research has demonstrated the validity of this approach, including capturing “real-time” data beyond what can be captured with retrospective reports. Surveys (<1 minute each) will be electronically collected once a week for the 6 weeks of the intervention period starting one week after randomization (i.e., 6 electronic survey entries), leading up to the 3-month follow up. With input from the CAB, we have established procedures to auto-send an email or SMS text (participant choice) on a set schedule. SMS text messaging is possible via Twilio, embedded within our REDCap system, which allows participants to complete a survey directly from their phone, without having to access a webpage. Participants will be asked permission for the study team to access electronic medical records to collect CD4 count and viral load at the time of enrollment. As an attending physician in the clinic, Co-I [name] is familiar with these electronic records and will oversee the data pull. CD4 T-cell counts and HIV viral load will be measured as standard clinical practice using standard clinical assays (HIV viral load less than 200 considered virologic suppression). Relevant data from the clinic’s electronic medical record (e.g., CD4 count, no-shows) will be collected at intervals and study completion (i.e., 6 months after participation) to document retention in HIV clinical care using the industry standard of 2 appointments with a provider with prescribing privileges per year, no longer than 6 months apart. PI [name] has planned for adequate staff training and coverage based on experience. The PI will assist in training research staff on consent, diagnostic interview, assessment measures, and medical chart data retrieval (with Co-I [name] and Co-I [name] for service utilization data) and will conduct weekly meetings, quarterly reviews, and booster trainings to ensure standardized procedures. See Table 2 for research instruments.

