Support Electronic Survey	P	x	x	x		Captures more ecologically valid data than retrospective recall at three data assessment points (0, post intervention, 3 month follow up), support services will be collected via REDCap survey from baseline until 3 month follow up across both conditions.
Electronic Medical Record Data						
CD4 count	PC	x	x	x		We will use clinic lab test (standard clinical assays) results for our data.
HIV care appointment adherence †	PC	x		x		Electronic medical record data coding at end of study for clinic appointment attendance with a provider with prescribing privileges
Viral load	PC	x	x	x		We will use standard clinical assays (collected for clinical purposes). An HIV viral load less than 200 will be considered consistent with virologic suppression.

Services Chart Review	PC	x	x	x		PC will use the same Services Tracking Form to capture data on service utilization entered by case managers of SOC and CPT-L participants in the electronic medical record.
Treatment Assessment						
Clinician Survey on PTSD	PC	x	x	x		Assesses therapist experience and attitudes (completed by the project therapist before training, after training, and at 3-month intervals throughout the trial)
Therapist Fidelity Checklist	CM				x	Checklist used by Drs. [name] and [name] in CPT and Lifesteps protocol studies.
Reactions to Treatment						
Client Satisfaction Questionnaire-8	P		x			Likert scale with 8 items that has been standardized to investigate client satisfaction.
Acceptability	P		x			At the first assessment following treatment graduation or discontinuation, participants will complete a survey (1 = strongly disagree to 4 = strongly agree) on their satisfaction (with intervention, therapist, frequency, length of sessions, with amount of confidentiality and respect received); ratings of usefulness of each session; perceived barriers, general experience with the study, likelihood of recommending the study to other patients, and suggestions for improving treatment.
Working Alliance Inventory-Short Revised (WAI-SR)	P		x		x (wk 3; mid treatment)	Assesses three key aspects of the therapeutic alliance: (a) agreement on tasks of therapy, (b) agreement on goals of therapy and (c) development of an affective bond.

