#### **14.0 Withdrawal of Subjects**

Participants may voluntarily elect to withdraw their consent at any time for any or no given reason while enrolled in the study. The PI may withdraw participants from the study at any time if they decide it is in

the participant's best interest, if they do not follow the investigator's instructions, and/or if they fail to maintain to contact with the researchers or attend study visits. Withdrawals of participants may also occur if there is a protocol violation or early study closure. All data gathered from withdrawn participants will be used in the analysis plan under an Intention-to-Treat (ITT) model.

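### The CD4 and HIV symptom comparison has no visit or subject term and no missing-data method; run in the natural way it leaves post-intervention data unused and can be biased in either direction

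*Combined protocol and SAP*

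**What the plan says.** Section 12.0 (Data Analysis Aim 2) says that HIV symptom distress, CD4 count and the other HIV outcomes "will be measured at pre- and post-intervention and 3-month follow-up". It expects treatment to change CD4 and "symptom severity more so in the CPT-L group compared to Lifesteps at the follow up clinic visit". The next sentence gives the method: "Treatment group differences will be assessed using generalized linear models adjusted for baseline cell counts/symptom scores". That sentence names no visit, within-person correlation or rule for missing values.

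Neighbouring outcomes are specified more fully. The binary HIV outcomes get a modified Poisson model with visit and visit-by-treatment terms. For the text that follows on CAPS-5 and PCL, "Rates of change from baseline to post-intervention and follow up will be estimated with generalized linear mixed effects regression models". AUDIT, DAST and PROMIS depression also get mixed models. The same paragraph adds: "Estimated CAPS, PCL, and HIV symptom severity scores and associated standard error estimates will be calculated for each study group at each study visit". CD4 is not in that list.

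On loss of participants, section 14.0 states: "All data gathered from withdrawn participants will be used in the analysis plan under an Intention-to-Treat (ITT) model". Section 10.0 states: "All timepoints will be collected on all participants, even if they drop out of treatment". Table 2 says of CD4: "We will use clinic lab test (standard clinical assays) results for our data". Imputation is mentioned only under Data Resource Sharing, without a method.

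**The concern.** A baseline-adjusted regression on the 3-month value uses only people who have that value. Someone measured after the intervention (about 6 weeks after enrolment) and then lost contributes nothing to the arm difference, although their post-intervention result has been collected and predicts the missing one. Section 14.0 promises to use such data, and section 12.0 gives no method that does so for this comparison.

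HIV symptom distress is one of the outcomes in hypothesis (a) of Aim 2, and the estimates are meant to inform the later efficacy trial. CPT-L is twelve 90-minute sessions and Lifesteps is one, so unequal loss between arms is plausible, though the documents do not predict it. If loss also depends on how people were doing after the intervention, the arm difference carried forward could be too large or too small.

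**Working it through.** **Inputs from the documents.** 60 participants, 30 per arm; stated precision 0.51 SD for continuous outcomes (section 12.0); retention targets of 80% (section 1.0) and 90% (section 12.0, Data Analysis Aim 2).

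**The plan's own figure.** The 95% half-width for a difference in means is 1.96 × √(2/n) SD.

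- n = 30 per arm: 1.96 × √(2/30) = 0.506, which reproduces the stated 0.51. It requires all 60 to contribute.
- n = 27 per arm (90% retained): 0.533.
- n = 24 per arm (80% retained): 0.566.

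**Bias: assumed inputs.** The documents give no loss rates by arm and no correlations, so these are assumptions. Scores have unit SD and the true arm difference is -0.50 SD at both post-baseline visits (negative means a lower score in CPT-L). Correlations are 0.6 (baseline with post-intervention), 0.7 (post-intervention with 3 months) and 0.5 (baseline with 3 months). Loss occurs after the post-intervention visit and before 3 months. Where loss is informative, its log-odds rise by 0.8 to 1.5 per SD of a worse post-intervention score.

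**Two estimators.**

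1. Complete-case: regress the 3-month value on arm and baseline, among those with a 3-month value.
2. Likelihood, using the post-intervention value: (a) regress the 3-month value on arm, baseline and post-intervention value among those observed, giving arm coefficient g₁ and post-intervention coefficient g₂; (b) regress the post-intervention value on arm and baseline in everyone, giving arm coefficient h₁. The arm difference is g₁ + g₂ × h₁.

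**Results by simulation (true value -0.50 SD).**

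| Loss CPT-L / Lifesteps | Who leaves | Complete-case |
|---|---|---|
| 23% / 10% | poor responders in CPT-L; random in Lifesteps | about -0.57 to -0.61 |
| 10% / 10% | poor responders in CPT-L (log-odds 0.8); random in Lifesteps | -0.53 |
| 23% / 10% | poor responders in both arms | about -0.54 to -0.56 |
| 17% / 17% | poor responders in both arms alike | -0.50 |
| 10% / 23% | poor responders in both arms | -0.46 |
| 10% / 23% | random in CPT-L; poor responders in Lifesteps | -0.42 |

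The likelihood estimator gives about -0.50 in every row. At 23% and 10% loss, overall retention is (77 + 90)/2 = 83.5%, between the plan's two targets.

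**Relative size.** The largest overstatement is (0.605 - 0.50)/0.50 = 21%; the largest understatement is (0.50 - 0.42)/0.50 = 16%. Against the plan's half-width, 0.11/0.51 is about one fifth.

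**Precision.** In simulated trials of 60, the SD of the estimate was 0.245 for the likelihood estimator and about 0.25 for complete-case, so using the extra visit cost no precision.

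**Limit of the remedy.** In a separate run (all correlations 0.5, 20% loss per arm, random in Lifesteps), loss in CPT-L depended on the unseen 3-month value itself. Complete-case gave -0.70 and the likelihood estimator -0.68, so the mixed model does not correct that kind of loss.

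**The case against.** The strongest reply is that the sentence names no visit and no deletion rule. The follow-up visit belongs to the preceding hypothesis, and the modified Poisson models show that the authors fit visit terms in models they do not call mixed. This is fair: a single-visit analysis is the natural reading, not a stated one. But if both visits were meant to be stacked, a generalized linear model with no stated within-person correlation would give unreliable standard errors, so that reading also needs correction.

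Second, HIV symptom severity may already be covered, since its per-visit estimates are listed after the mixed-model text. That narrows the point but leaves two possible models for one symptom difference and no rule for which counts. It does not help CD4.

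Third, missing values may be few. Assessments continue after treatment dropout, and CD4 comes from clinic records. Both reduce missingness. Neither covers withdrawn consent or lost contact, which sections 4.0 and 14.0 anticipate. CD4 is available only if the clinic ordered it, and the entry criteria include missed appointments and a last visit more than 6 months ago.

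Fourth, the sizes rest on assumed loss and are small beside a half-width of 0.51 SD in a pilot sized on pragmatic grounds. That stands, and it limits the weight of the point.

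A reader might also infer that the plan will overstate CPT-L whenever poor responders leave. The documents do not support that: the direction depends on which arm loses them, and similar loss in both arms gives no bias.

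**Conclusion.** The point holds as a gap in specification with a better method readily available. The CD4 and HIV symptom comparison has no visit or subject term and no missing-data method. On its natural reading it leaves collected post-intervention data unused.

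It would go too far to say that the plan contradicts section 14.0 or announces that participants will be dropped. Section 14.0 makes a promise, and section 12.0 lacks a method to deliver it here.

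Under the assumed conditions the error ranges from about 0.11 SD too large to 0.08 SD too small for a true 0.50 SD, and is nil when loss is alike in both arms. These figures rest on assumed loss rates, correlations and dependence on the post-intervention result. The conclusion is firm for CD4. For symptom severity it depends on which of the two described models supplies the arm difference.

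**What to change.** For both outcomes, take the arm difference at post-intervention and at 3 months from one baseline-adjusted repeated-measures mixed model:

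- Responses: the post-intervention and 3-month values.
- Terms: arm, visit, arm-by-visit, baseline, baseline-by-visit, and the urn variables (viral load and self-identified gender).
- Unstructured covariance between the two visits.
- All randomised participants with any post-baseline value.

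State that this model, and no other, gives the reported arm difference for HIV symptom severity. State that it assumes data are missing at random given arm, baseline and observed values. Add a simple sensitivity analysis, for example shifting imputed 3-month values by a stated range separately in each arm. This is needed because the model does not correct loss that depends on the unseen 3-month value, and it recovers nothing for participants who also miss the post-intervention visit. Reconcile the 80% and 90% retention targets, since they imply different amounts of missing data.

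The cost is a few lines of plan text and SAS code. No new data, visits or participants are needed.
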